### 2. Inclusion Criteria

Participants must meet all of the following inclusion criteria to be eligible for participation in this study.

1. Written informed consent has been provided by the participant /parent or legal guardian.
2. Participants (of any gender and any race) aged  $\geq 5$  years to  $\leq 25$  years at time of screening.
3. The participant has confirmed, active EoE (within 12 weeks prior to enrollment) as defined by esophageal mucosal eosinophils  $\geq 15$  per HPF (400 x magnification) confirmed by the research pathologist AND fits into one of the following categories:
  - a. Participant has not been diagnosed with and does not display phenotypes suggestive of a CTD, or
  - b. Participant has been diagnosed with a CTD (e.g., MFS, LDS, EDS, or hypermobility syndromes).
4. The participant has been on a high dose of PPI (at least one dose, once daily) for at least 8 weeks prior to a diagnostic endoscopy of EoE without histologic resolution (i.e.,  $\geq 15$  eosinophils/HPF). Due to the variety of doses and various PPIs available, the dose will be confirmed adequate at the discretion of the site PI.  
Note: Participants may continue with their acid reflux therapy as long as the dose remains the same throughout the study.
5. Participant must maintain the same diet, swallowed steroid, and PPI therapies throughout the duration of the study. Participants with active EoE on these therapies may be included in the study, as long as they agree to maintain the same diet, swallowed steroid, and PPI therapies.
6. At the time of study entry, a female participant is eligible if she meets one of the following criteria:

- a. Is of non-childbearing potential (pre-menarchal or surgically sterile with documentation);
- b. Is of childbearing potential with a negative urine pregnancy ( $\beta$ -hCG) prior to enrollment into the study (i.e., at screening) and at each study visit. Subsequently, these participants must agree to use adequate birth control measures (e.g., condom, oral / injectable / subcutaneous contraceptives, intrauterine device, or sexual abstinence) during the study and for at least one month after the last dose of study drug, which will be documented in the source documents.

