#### 5. Premature Discontinuation of Investigational Agent

Study therapy may be prematurely discontinued for any participant for any of the following reasons:

- Occurrence of an AE that, in the opinion of the investigator, requires the participant's permanent withdrawal from the study agent. In the event of withdrawal from the study agent due to the occurrence of a SAE, the Investigator and Sponsor must be notified within 24 hours (See section 11.7). A participant withdrawn secondary to an ongoing SAE that is considered possibly or probably related to the study agent must be followed clinically until resolution or stabilization of the SAE.
- Insufficient therapeutic effect requiring alternative or additional therapy for the treatment of EoE, including the need for "rescue" systemic or swallowed inhaled corticosteroid therapy, in addition to the study agent, for the treatment of the current EoE. Criteria for withdrawal due to lack of efficacy will rely on the best clinical judgment of the PI that the participant requires a new therapeutic intervention due to the clinical state of his/her EoE. Examples would include: worsening of the presenting predominant symptom of EoE, the emergence of a new additional symptom of EoE that is at least moderate in intensity and is due to EoE, or the need for new systemic treatment (e.g., oral corticosteroids). In contrast, small dietary modifications or modest increases in symptom frequency without increased severity would not constitute withdrawal criteria.
- Study therapy may also be prematurely discontinued for any participant if the investigator believes that the study treatment is no longer in the best interest of the participant.

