#### 8.8 Visit 6 End-of-Treatment (EOT) or Early Withdrawal (Week 16 $\pm 7$ days) Visit

For participants who have completed the maintenance phase or who have withdrawn early from the study, the following procedures will be performed in the clinic:

- Conduct vitals (blood pressure, heart rate, respiratory rate, temperature), height, and weight
- Physical exam
- Administer patient- and parent-reported outcome questionnaires
- Clinical laboratory samples, including CBC with differential, chemistry, and IgE
- Research laboratory samples

- Urine pregnancy test in females of childbearing potential
- Assess AEs
- Assess changes to concomitant medication/therapies
- Obtain esophageal biopsies including biopsies taken for clinical purposes and up to 4 biopsies from the distal esophagus for research purposes obtained from standard of care (SOC) endoscopy
- Assess participant compliance with diet
- Collect diet and medication log
- Collect study agent bottle and unused study agent
- Determine participant's compliance with the study agent

The EOT visit may be divided into two appointments, if necessary, in order to allow for all necessary procedures to be performed. Participants who have completed the maintenance phase should be instructed not to take the study agent on the day of this visit; the last dose of study agent should be taken the day prior to the EOT visit. If a participant withdraws from the study before completing the maintenance phase, the EOT/early withdrawal visit, including EGD and biopsy, should be conducted within one week of the participant's last dose of the study agent.

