### 3. Participant Replacement

Enrolled participants who receive the study agent and prematurely discontinued or withdraw from the study will be replaced if they do not reach Week 16 of the study, including the EOT visit (EGD). Additional participants will be enrolled in the same manner as all other participants. Participant numbers will not be re-used. Any enrolled participant will be included in the intent-to-treat analysis.

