This is a phase II, open-label trial of losartan in patients diagnosed with EoE with or without a CTD. Prior to entry, patients must meet the current consensus criteria for EoE in which efforts are made to rule out other causes of esophageal eosinophilia. The trial will perform a preliminary assessment of the effect of the maximum tolerated dose of losartan in participants with active EoE as determined by the absence of side effects and by vital signs being within normal limits. The primary endpoint of the study is the reduction in the number of esophageal eosinophils in participants who will receive losartan orally once a day (Figure 1). The primary safety endpoint is descriptive and will require reporting of SAE or Grade 3 and above AEs.

Figure 1 Study Design Flowchart

Analysis Populations

The analysis population for the primary and secondary endpoints will be participants who received Losartan and maintained the baseline EoE treatment throughout the course of the study.

Statistical Considerations and Analytical Plan

Overview

Change from baseline for eosinophil counts will be calculated for each participant. The average change from baseline within each group and combining both groups (i.e. EoE and EoE-CTD) will be calculated along with the corresponding two-sided, 95% confidence interval. Additionally, we will perform paired tests which will specifically test whether there was significant change between baseline and study completion. The last observation carried forward (LOCF) method will be used for participants who end the trial early. To assess changes over time for continuous secondary and safety outcomes, a mixed effects model for repeated measures analysis will be used. Unless stated otherwise, all statistical testing will be done at $\alpha=0.05$.

Variables of Interest

Primary outcome:

- 1) Change in eosinophils/hpf from baseline to post treatment
- 2) Rate of SAE / Grade 3 or above AE

Secondary outcomes:

- 1) Blood (serum) and esophageal TGF- β levels
- 2) EoE transcriptome
- 3) Histopathology as assessed by the Histology Scoring System (HSS): Will include the overall score, grade score, stage score, and the inflammatory and structural sub-scores. Scores will be reported as distal, proximal, and maximum
- 4) Esophageal compliance as measured by EndoFLIP.
- 5) PROS (Pediatric Eosinophilic Esophagitis Symptom Severity [PEESS], PedsQL Eosinophilic Esophagitis Module [PedsQLTM EoE], EoE Quality of Life Questionnaire, and EEsAI)

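### The SAP's only efficacy analysis set requires maintained baseline EoE treatment, which conflicts with the protocol's intent-to-treat statement and can leave out treated participants who needed other therapy

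*SAP*

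**What the plan says.** The SAP (Analysis Populations) gives a single population for the primary and secondary endpoints: "participants who received Losartan and maintained the baseline EoE treatment throughout the course of the study". It names no intent-to-treat or all-treated set, and no sensitivity analysis in a wider set.

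Protocol section 10.3 has treated participants who leave before the Week 16 endoscopy replaced, and then states: "Any enrolled participant will be included in the intent-to-treat analysis". That is the protocol's only use of the term; section 12 does not develop it.

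Four other provisions bear on who falls inside the SAP set:

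- Protocol section 6.5 lists as a reason for stopping study therapy: "Insufficient therapeutic effect requiring alternative or additional therapy for the treatment of EoE". It adds that "small dietary modifications or modest increases in symptom frequency without increased severity would not constitute withdrawal criteria".
- Protocol section 4.2, criterion 5, requires that "Participant must maintain the same diet, swallowed steroid, and PPI therapies throughout the duration of the study". This is the likely meaning of baseline EoE treatment in the SAP, but the SAP neither cites it nor says what departure counts.
- Protocol section 8.8 says that for a participant who withdraws early "the EOT/early withdrawal visit, including EGD and biopsy, should be conducted within one week" of the last dose. Table 4, footnote f, allows two weeks. Section 3.3 defines the primary endpoint at end of treatment or at early withdrawal.
- The SAP (Overview, and again under the primary outcome) states: "The last observation carried forward (LOCF) method will be used for participants who end the trial early".

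**The concern.** Membership of the SAP set is decided by something that happens after treatment starts. One route out of the set is adding or changing EoE therapy because losartan was not working. If such participants are left out, the estimated change describes people who did not need other treatment, not everyone given the drug. The trial has a single arm, so there is no control group in which the same selection would show.

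The protocol promises an analysis that keeps these participants, and the SAP as written does not deliver it. Section 12.5 of the protocol says the estimates will be used to power future studies, so a selected estimate could carry into the sizing of the next trial. The smaller group, EoE-CTD with 5 planned, is the more sensitive to one exclusion.

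The undefined term adds a practical problem. A participant with a small diet change need not be withdrawn under section 6.5, yet the SAP does not tell the analyst whether that person maintained baseline treatment.

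**Working it through.** **Setting the texts side by side**

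| Participant | Protocol 10.3 | SAP set |
|---|---|---|
| Received losartan, kept baseline therapy, completed Week 16 | In | In |
| Stopped early, kept baseline therapy, biopsied before any new therapy | In | Probably in; LOCF or the withdrawal biopsy then applies |
| Added or changed EoE therapy for insufficient effect, withdrawal biopsy available | In | Out, if the change counts as part of the course of the study |
| Completed Week 16 with a small diet change | In | Unclear |
| Enrolled, never took losartan | In | Out |

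The two documents part company in the last three rows.

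**Inputs**

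- Planned numbers: 15 pooled, 10 EoE, 5 EoE-CTD (protocol 12.5).
- SD of the change on the square-root scale: about 5 (protocol 12.5).
- Number excluded: not given; one is assumed.
- Difference *d* between that participant and the mean of the others: not given; 1 SD = 5 is assumed.

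**Reproducing Table 7.** Half-width = t(0.975, n−1) × 5 / √n.

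- n = 15: 2.77 (Table 7: 2.8)
- n = 10: 3.58 (Table 7: 3.6)
- n = 5: 6.21 (Table 7: 6.2)

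**Effect of one excluded participant.** A treated participant who leaves before Week 16 is replaced, so the SAP set keeps its planned number and the all-treated set has one more: N = 16, 11 or 6. If the others have mean m and the extra participant has m + d, the all-treated mean is [(N−1)m + (m + d)] / N = m + d/N. The two analyses therefore differ by d/N:

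| Group | N all-treated | d/N with d = 5 | Planned half-width |
|---|---|---|---|
| Pooled | 16 | 5/16 = 0.31 | 2.8 |
| EoE | 11 | 5/11 = 0.45 | 3.6 |
| EoE-CTD | 6 | 5/6 = 0.83 | 6.2 |

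One participant affects the pooled figure and one of the two subgroup figures, not both.

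**When only the baseline biopsy exists.** Endoscopy is scheduled only at screening and at end of treatment or early withdrawal (Table 4), so LOCF then gives a change of zero, and *d* is the size of the mean change in the others. An assumed mean of −5 reproduces the figures above. An assumed mean of −2 gives 2/16 = 0.13, 2/11 = 0.18 and 2/6 = 0.33. A mean of −5 is a large fall: it takes a count of 64 to 9 (8 − 5 = 3, squared), and a participant entering at 15 per HPF cannot fall by more than √15 = 3.9.

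**The case against.** The best defence is that stable diet, swallowed steroid and PPI are a condition of the design. In a single-arm open-label trial there is no randomised comparison for intent-to-treat to protect, and a fall in eosinophils after a new steroid or diet cannot be credited to losartan. An all-treated analysis would admit some of those biopsies, and the two-week allowance in Table 4, footnote f, leaves more time for new therapy to act than the one week in section 8.8. This stands as a reason to keep the maintained-treatment set in view. It also means that which set should lead is a matter of judgement. It does not justify having only that set when the protocol says otherwise.

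A reader might infer that the SAP set drops everyone who stopped for insufficient effect. The documents do not go that far. Section 6.5 concerns stopping losartan, and sections 8.8 and 10.4 then call for end-of-treatment procedures at withdrawal. Someone biopsied on unchanged baseline therapy can reasonably be counted as having maintained it.

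A reader might also infer that the LOCF rule contradicts the set. It does not: LOCF can apply to early leavers who kept their baseline treatment. It cannot bring in a participant who is outside the set.

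Finally, the trial is a pilot whose size was not based on power, and the illustrated shifts sit well inside its planned imprecision. That is correct and limits the weight of the point.

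**Conclusion.** The conflict is real. The SAP's sole set for the primary and secondary endpoints is narrower than the intent-to-treat analysis in protocol section 10.3. It rests on a post-baseline event that can follow from poor response, and it does not define that event. Treated participants who added or changed EoE therapy can be left out even when a withdrawal biopsy exists.

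The size is likely to be modest. Under the assumptions of one excluded and replaced participant and a 1 SD difference, the mean moves by 0.31 pooled, 0.45 in EoE or 0.83 in EoE-CTD. That is about 11%, 13% and 13% of the planned half-widths (0.31/2.8, 0.45/3.6, 0.83/6.2). More exclusions, or a larger difference, would increase it.

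It would go too far to conclude that the plan overstates losartan's effect. Leaving out participants with insufficient effect would tend to overstate the reduction, but including someone biopsied after starting a steroid could overstate it too. The documents give no frequency for either, so the direction and size of any bias are unknown. The SAP should be corrected because the remedy is cheap and restores what the protocol states.

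**What to change.** In the SAP:

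1. Add, as the protocol's intent-to-treat analysis, an analysis of all enrolled participants who received losartan, including those who were replaced and those who changed diet or EoE therapy. Use the end-of-treatment or early-withdrawal biopsy where there is one and LOCF otherwise, and state that LOCF gives a change of zero when only the baseline biopsy exists.
2. List any enrolled participant who never took losartan. This is the one stated departure from section 10.3.
3. Report the maintained-treatment set beside it, and say in advance which of the two leads.
4. Define maintained by inclusion criterion 5 and state what departure counts, including small diet changes. Classify departures from the diet and medication logs and the deviation forms, without sight of the end-of-treatment eosinophil counts.

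The cost is SAP wording, one classification step on records the protocol already collects, and one additional run of the analysis. No new visits or data are needed. The downside is that the all-treated estimate may contain some effect of changed background therapy; the maintained-treatment result beside it lets the reader judge how much.

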### 3. Primary Endpoint(s)/Outcome(s)

- Change from baseline in the peak esophageal eosinophil count in participants receiving losartan potassium at the end-of-treatment (EOT) visit (or at early withdrawal) as determined by esophagogastroduodenoscopy (EGD) with biopsy and reported as eosinophils per high-power field (eosinophils/HPF).
- A primary safety endpoint is also included to monitor for adverse events in the enrolled subjects. Specifically, as a descriptive investigation, any SAE or Grade 3 and above AEs that arise during the conduct of this pilot study will be reported.

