## 8 Study Procedures

### 1. Visit 1 Screening/ Baseline Visit (Week -12 to 0)

#### Recruitment

The research study will be explained in lay terms to each potential research participant. Participants will be recruited from the gastroenterology, allergy, or other clinics at each study site when potential participants with EoE and CTD may be seen. Participants who receive care from other institutions that express interest in participating may be enrolled in the study. The PI and the study staff team will work with the participant's primary care physician to explain the study objectives and requirements for the study. If the participant's primary care physician agrees that the participant would be a good candidate for the study, study staff will contact the participant and carry out all recruitment and screening procedures. In addition, potential participants will be identified through the EGD database (CCHMC IRB studies #2008-0090 and 2008-0098), as well as other databases and resources at each study site. Research staff will pre-screen or identify potentially eligible participants by conducting a review of existing medical and/or research records and IRB-approved recruitment materials.

The clinical trial information will be entered into a databank on [www.clinicaltrials.gov](http://www.clinicaltrials.gov) maintained by the U.S. National Library of Medicine (NLM) at the National Institutes of Health (NIH) or other websites.

The purpose of the screening period is to confirm eligibility to participate in the study. The screening visit should occur at a maximum of 12 weeks prior to the enrollment visit. The research staff member will perform the informed consent process according to Section 19. After obtaining informed consent, the following study assessments/procedures should be performed and documented up to 12 weeks prior to the enrollment (Week 0) visit or during the enrollment visit:

- Eligibility (inclusion and exclusion criteria)
- Medical, surgical and diet history
- Conduct vitals (blood pressure, heart rate, respiratory rate, temperature), height, and weight
  - Demographics (age, gender, race)
  - Physical exam performed by a study clinician
  - Clinical laboratory samples, including CBC with differential, chemistry, and IgE
  - Research laboratory samples (See Table 4)
  - Urine pregnancy test for females of childbearing potential
  - Concomitant medications and therapies

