### **Activities of Daily Living (ADL)**

\*Instrumental ADL refers to preparing meals, shopping for groceries or clothes, using the telephone, managing money, etc.

\*\*Self-care ADL refers to bathing, dressing and undressing, feeding self, using the toilet, taking medications, and not being bedridden.

The study site will grade the severity of AEs experienced by the study participants according to the criteria set forth in the NCI-CTCAE manual (Version 4), which provides a common language to describe levels of severity, to analyze and interpret data, and to articulate the clinical significance of all AEs. The NCI-CTCAE manual has been reviewed by [REDACTED] and has been deemed appropriate for the participant population to be studied in this protocol.

For grading an abnormal value or result of a clinical or laboratory evaluation (including, but not limited to, a radiograph, an ultrasound, an electrocardiogram etc.), a treatment-emergent adverse event is defined as an increase in grade from baseline or from the last post-baseline value that doesn't meet grading criteria. Changes in grade from screening to baseline will also be reported as adverse events, but are not treatment-emergent. If a specific event or result from a given clinical or laboratory evaluation is not included in the NCI-CTCAE manual, then an abnormal result would be considered an adverse event if changes in therapy or monitoring are implemented as a result of the event/result.

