## 6. Collecting and Recording of Adverse Events

### 1. Collection Period

AEs will be collected from the time after the participant signs informed consent/assent (Screening or Enrollment study visit) and will end after the cessation of the study agent (Week 20 [30 days after the last dose of the study agent]).

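### The primary safety rate has no all-dosed population and no counting window, so it can omit participants exposed to losartan and can include pre-dose events

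*SAP*

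**What the plan says.** **Outcome.** SAP, Variables of Interest, gives the second primary outcome as "Rate of SAE / Grade 3 or above AE", with no numerator, denominator, time unit or window. Protocol section 3.3 describes the same endpoint as descriptive: "any SAE or Grade 3 and above AEs that arise during the conduct of this pilot study will be reported".

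**Population.** SAP, Analysis Populations, has one definition: "The analysis population for the primary and secondary endpoints will be participants who received Losartan and maintained the baseline EoE treatment", for the whole study. No safety set appears in either document. Protocol section 10.3 places everyone enrolled in an intent-to-treat analysis. The closing lines of the SAP's analysis text, like protocol section 12.4, promise a descriptive account of SAEs and Grade 3+ events and name no population.

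**Change of EoE therapy.** Protocol section 6.5 foresees that some participants will need additional or alternative EoE treatment while on losartan, and makes this a possible reason to stop the study agent.

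**Window.** Protocol section 11.6.1: "AEs will be collected from the time after the participant signs informed consent/assent", ending 30 days after the last dose. Section 8.1: "The screening visit should occur at a maximum of 12 weeks prior to the enrollment visit". Section 8.2 allows the two visits to be combined. Table 4 has no AE-assessment mark at Screening; the first is at Visit 2. The text after Table 5 says of pre-dose changes: "Changes in grade from screening to baseline will also be reported as adverse events, but are not treatment-emergent". That text concerns the grading of abnormal clinical or laboratory results.

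**The concern.** A safety rate should answer a simple question: of the people who took the drug, how many had a serious or severe event? The SAP's population rule adds a condition that can only be judged after dosing, namely whether EoE therapy stayed the same. That condition may suit a histology endpoint, where added steroid would confound the eosinophil count. For safety, it removes exposed people because of how they fared after exposure.

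The missing window is a second, smaller gap. Two analysts could each follow the SAP and differ on whether an event during screening counts. Such events are plausible: protocol section 11.7.3 describes food impaction and esophageal dilation as common in this population.

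At stake is the only numerical summary of the primary safety outcome in a trial so small that one participant's classification changes the result visibly.

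**Working it through.** There is no planned safety figure to reproduce. Protocol section 12.5 gives interval widths for the eosinophil change and for binary endpoints, but no expected event rate.

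**1. Population: the texts side by side**

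| Source | Who is covered |
|---|---|
| SAP, Analysis Populations | Received losartan and kept baseline EoE treatment; applies to primary and secondary endpoints |
| Protocol 10.3 | Everyone enrolled (intent-to-treat) |
| Protocol 3.3 and 12.4; SAP closing analysis text | Any such event, no population named |

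The safety rate is a primary outcome, so the first row governs it. The third row supports a listing but supplies no denominator. The second row contradicts the first. Section 10.3 also replaces dosed participants who do not reach Week 16, so a participant who stops because of added EoE therapy may be both outside the SAP population and replaced by someone else.

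**2. Size of the population effect**

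Input from the documents: n = 15, made up of 10 EoE and 5 EoE-CTD (protocol 12.5). The event counts below are assumptions, since the documents give none. Rate = participants with an event / participants in the set.

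- All dosed, two with events: 2/15 = 13.3%.
- One participant with an event dropped: 1/14 = 7.1%.
- Both participants with events dropped: 0/13 = 0%.
- Two participants without events dropped: 2/13 = 15.4%.

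The shift can go either way. Categorical safety endpoints are also summarized by group. Among 5 EoE-CTD participants, one event is 1/5 = 20%; if that participant is dropped, the rate is 0/4 = 0%. If replacement raises the number dosed above 15, each shift is somewhat smaller.

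**3. Size of the window effect**

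Inputs: treatment about 16 weeks (protocol synopsis); follow-up 30 days = 30/7 = 4.3 weeks; screening-to-enrollment gap from about 0 to 12 weeks (protocol 8.1 and 8.2). Time from first dose to end of collection = 16 + 4.3 = 20.3 weeks. Pre-dose share = gap / (gap + 20.3).

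| Gap (weeks) | Pre-dose share of collection time |
|---|---|
| 0 | 0% |
| 4 | 4/24.3 = 16.5% |
| 8 | 8/28.3 = 28.3% |
| 12 (maximum) | 12/32.3 = 37.2% |

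To put this on the scale of the rate, assume a constant background risk q per participant over the 20.3 weeks (no rate is given in the documents). With the pre-dose gap counted, the risk becomes 1 − (1 − q)^((20.3 + gap)/20.3).

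| Assumed q | 4-week gap | 12-week gap |
|---|---|---|
| 5% | 6.0% | 7.8% |
| 10% | 11.9% | 15.4% |
| 20% | 23.4% | 29.9% |

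These figures apply only if pre-dose events are counted, which the SAP neither requires nor rules out.

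**The case against.** The strongest reply is that the endpoint is descriptive, the trial is small, and both documents say that any SAE or Grade 3+ event will be reported. All SAEs must be entered whatever their relationship to the drug (protocol 11.7), and onset date, severity and relationship are recorded for each event (11.6.3). A reader could therefore check each case. This stands as far as it goes: a complete listing is likely. It does not repair the rate, which the SAP names as a primary outcome and which still needs a numerator and a denominator.

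Several stronger readings are tempting, and the documents do not support them:

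- *The rate counts from consent.* Section 11.6.1 sets a collection period, not a counting rule. The SAP states no counting window, and Table 4 starts AE assessment at Visit 2. The defect is an undefined window.
- *The rate does not measure safety on losartan.* Even at the 12-week maximum, 20.3 of 32.3 weeks (63%) is on drug or within 30 days after it. The population requires receipt of losartan, so events in screen failures cannot enter.
- *On-drug events are lost.* They may leave the rate, but the descriptive report should still contain them.
- *Those excluded are likelier to have had events.* This is plausible but not quantified. Section 6.5 ties added EoE therapy to insufficient effect, which is not in itself an SAE or Grade 3+ event. Stopping losartan for an adverse event does not by itself exclude anyone.
- *The protocol already has a treatment-emergent definition that the SAP ignored.* That definition covers graded clinical or laboratory results, not all adverse events.

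**Conclusion.** The concern holds in a limited form. As written, the SAP's single population removes dosed participants from the primary safety rate if their EoE therapy changed, in conflict with protocol section 10.3 and in tension with the promise to report any event. On assumed counts in 15 participants, a true 13.3% could be shown as anything from 0% to 15.4%, depending on who is dropped. How many would be dropped cannot be known from the documents.

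The missing window is secondary. The pre-dose share of collection time runs from 0% with combined visits to 37% at the longest permitted gap, and its effect on the rate depends on an unstated background risk.

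The imprecision that comes from the sample size is a separate matter. One event in 15 is 6.7 points, and 0/15 has an exact 95% upper limit of 21.8%; neither figure changes with the fix. For a descriptive pilot endpoint this is a correction that should be made, and it does not invalidate the trial.

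**What to change.** In the SAP:

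1. Add a safety population: every participant who took at least one dose of losartan, whether or not EoE therapy later changed, including participants who were replaced.
2. Define the primary safety outcome as the number and proportion of that population with at least one SAE or Grade 3+ AE whose onset or worsening falls between the first dose and 30 days after the last dose.
3. List pre-dose events separately.
4. Keep the maintained-therapy population for efficacy only, if at all, and reconcile it with the intent-to-treat statement in protocol section 10.3.
5. Reconcile protocol section 11.6.1 with Table 4 on when AE assessment starts.

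An exact 95% interval for the proportion is optional and corrects no error.

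The cost is wording. Onset and end dates and severity are already recorded for each event (protocol 11.6.3), so no new data are needed. The one practical check is that a worsening to Grade 3 carries its own date in the database.
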